### 12.1.2 24-hour Cough Frequency

The secondary efficacy endpoint of 24-hour cough frequency will be calculated as:

- 24-hour cough frequency = (total cough count/duration of measurement [hour])

The 24-hour average cough count (per hour) will be calculated using the total number of coughs divided by the total duration.

The 24-hour cough frequency after the 2-week treatment will be analyzed using the same methods described for the key secondary efficacy endpoint, including the subgroup analysis by median, tercile and quartile classifications of the baseline awake cough frequency.

The analysis of change from baseline in 24-hour cough frequency will be repeated for the PP population.

### 12.1.3 Subgroup Analyses

Subgroup analyses may be performed to generate additional data in a population with baseline awake cough frequency of <25 and  $\geq 25$  coughs/hour.

Analysis for the cough frequency endpoints may be provided for the following subgroups of baseline factors:

- Awake baseline cough frequency (<25,  $\geq 25$  coughs/hour)
- Duration of cough (<10,  $\geq 10$  years)
- Potential comorbidities and medical conditions associated with cough (i.e. GERD, asthma, bronchitis)

- Cough modulating and cough-inducing medications, including proton pump inhibitors (omeprazole, pantaprazole), antihistamines (ranitidine, loratadine, cetirizine, fexofenadine, diphenhydramine), inhaled corticosteroids (fluticasone, mometasone), benzonatate, non-steroid anti-inflammatory drugs (ibuprofen), leukotriene receptor antagonists (singulair), statins, and trazadone. (Ding, et al., 2020)

## 12.2 Patient Reported Outcomes

[figure not shown]
### 12.2.1 Cough Severity using VAS

Participants will be asked to rate the severity of their cough over the past 24 hours using a 100 mm Cough Severity VAS single-item questionnaire with the response ranging from 0 ('No Cough') to 100 ('Extremely Severe Cough'). The cough severity will be measured using a 100 mm VAS. Subjects will be asked to rate their cough severity at Screening, Baseline (Day 1) and Day 14 of each treatment period. A score of  $\geq 40$  mm on the Cough Severity VAS at Screening is required for randomization into the study.

The changes from baseline in cough severity VAS scores (mm) will be analyzed using a similar approach described for the key secondary efficacy endpoint, including the subgroup analysis by median, tercile and quartile classifications of the baseline awake cough frequency, except that the scores will not be log-transformed prior to analysis.

The number and percentage of subjects with a  $\geq 30$ mm reduction from baseline, to Day 14, will be presented by treatment group.

The LSM changes from baseline will be presented for each treatment, and the treatment effect will be the difference between the LSM changes from baseline. The difference in LSM estimates and the corresponding 95% CIs and p-values will be presented.

### 12.2.2 LCQ and CQLQ Scores

A secondary efficacy endpoint includes the change from baseline in the LCQ and CQLQ total scores at end of each treatment period.

[figure not shown]
Subjects will complete the LCQ and CQLQ at Screening, Days 1 and 14 of each treatment period. A higher score indicates a better quality of life.

#### **LCQ Scores:**

The following three 7-point domain scores, total categories, and total score will be considered for summaries of the LCQ:

*LCQ (as collected on the eCRF)*

- Physical Score (*Range, 1 to 7*)
- Psychological Score (*Range, 1 to 7*)
- Social Score (*Range, 1 to 7*)
- Total Score (*Range, 3 to 21*)

### **CQLQ Scores:**

The CQLQ consists of 28 questions on a 4-point scale, and the following domain scores will be considered for summaries:

*CQLQ (scores calculated manually by adding the scores of the items listed)*

- Physical Complaints (Items: 4, 8, 10, 13, 14, 15, 17, 22, 23)
- Psychosocial Issues (Items: 1, 18, 24, 25, 27)
- Functional Abilities (Items: 2, 3, 19, 20, 21)
- Emotional Well-being (Items: 7, 9, 12, 16)
- Extreme Physical Complaints (Items: 5, 6, 11, 12)
- Personal Safety Fears (Items: 9, 26, 28)
- Total Score (Items: All)

Only two items, 9 and 12, are overlapped categories. Item 9 appears in the emotional well-being and personal safety fears category, and item 12 appears in the emotional well-being and extreme physical complaints categories.

[figure not shown]
If any individual item within a domain of the CQLQ is missing for a subject, the domain score will be considered missing for that subject.

Summary statistics of each domain at baseline and Day 14 and the change from baseline in each domain will be presented by visit and treatment group.

The changes from baseline (period baseline) in quality of life Total Score (measured by LCQ and CQLQ) will be analyzed using a similar approach described for the key secondary efficacy endpoint, including the subgroup analysis by median, tercile and quartile classifications of the baseline awake cough frequency, except that the scores will not be log-transformed prior to analysis.

The number and percentage of subjects with a  $\geq 1.3$  point increase from baseline, to Day 14, will be presented by treatment group.

The LSM changes from baseline will be presented for each treatment, and the treatment effect will be the difference between the LSM changes from baseline. The difference in LSM estimates and the corresponding 95% CIs and p-values will be presented.

to every

### 12.2.3 Global Rating of Change Scores for Cough Severity and Frequency

Subjects will complete the Global Rating of Change on Day 14 of each treatment period.

Subjects will rate the Change in Cough Frequency and Change in Cough Severity on the following scale:

- Worse
- About the Same
- Better

Frequency counts will summarize the Global Rating of Change scores and percentages for cough frequency and cough severity change scores separately for each treatment group. The difference between treatment groups, for the change, will be tested using the Cochran–Mantel–Haenszel (CMH) row mean score difference test. The p-value for the difference will be presented.

In addition to the change, the degree of change (for both cough severity and cough) frequency will also be provided on the following scale:

1. A Very Great Deal Better
2. A Great Deal Better
3. A Good Deal Better
4. Moderately Better
5. Somewhat Better
6. A Little Better
7. Almost the Same; Hardly Any Better at All
8. Almost the Same; Hardly Any Worse at All
9. A Little Worse
10. Somewhat Worse
11. Moderately Worse
12. A Good Deal Worse
13. A Great Deal Worse
14. A Very Great Deal Worse

[figure not shown]
The degree of change will be summarized by frequency counts and percentages for each treatment group.

Global rating of change scale will be remapped and given scores to create a continuous endpoint. A lower score will be considered a more positive outcome. The continuous endpoint will be summarized for each treatment group and appropriate hypothesis testing may be performed as a post-hoc analysis, if justified by the data.

All analyses will be repeated for the median, tercile and quartile group classifications based on the baseline awake cough frequency as described in the Key Secondary Efficacy Analyses Section.

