## 4.2.3 Secondary Endpoints

The secondary endpoints of this trial are:

- Change from baseline in 24-hour cough frequency per hour after 2-week treatment
- Change from baseline in cough severity using a visual analog scale (VAS)
- Change from baseline in LCQ scores
- Change from baseline in Cough-Specific Quality of Life Questionnaire (CQLQ) scores
- Global rating of change scores for cough severity and frequency
- Patient Global Impression of Change (PGIC) score
- Clinician Global Impression of Change (CGIC) score

CONFIDENTIAL Page 25 of 68

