#### 10.2 General Considerations

## 10.2.1 Statistical Hypotheses

The null  $(H_0)$  and alternative  $(H_1)$  hypotheses for the key secondary efficacy endpoint (awake cough frequency) can be expressed as:

 $H_0$ :  $\mu_{ADX} = \mu_{PLA}$  $H_1$ :  $\mu_{ADX} \neq \mu_{PLA}$ 

where  $\mu_{ADX}$  and  $\mu_{PLA}$  are the mean changes from baseline in cough frequency for ADX-629 and placebo respectively.

All statistical testing will be at the 5% level of significance (2-sided) and all point estimates for the comparison between treatment groups will be accompanied by 2-sided 95% confidence intervals.

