The changes from baseline in cough severity VAS scores and quality of life (evaluated with CQLQ) will be analyzed using a similar approach except that the scores will not be log transformed prior to analysis. Hence, mean changes from baseline will be presented, and the treatment effect will be the difference between the mean changes from baseline. The corresponding 95% confidence intervals and p-values will be presented.

Other efficacy endpoints will be summarized and analyzed to estimate the treatment effect and corresponding 95% confidence interval using a similar model to that described for awake cough frequency. Cough frequency endpoints will be analyzed on the natural log scale. Full details of analyses will be provided in the SAP, which will govern any statistical language within the protocol.

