## 8. GENERAL ANALYSIS CONSIDERATIONS

The statistical analyses will be reported using summary tables, listings, and figures (TLFs). The International Council for Harmonisation of Technical Requirements for Pharmaceuticals for Human Use (ICH) numbering convention will be used for all TLFs.

Unless otherwise noted, all statistical testing will be 2-sided and performed at the 0.05 significance level. Tests will be declared statistically significant if the calculated  $P$ -value is  $\leq 0.05$ .

Continuous variables will be summarized by presenting the number of observations, means, standard deviations (SDs), medians, minimums, and maximums.

Categorical variables will be summarized by presenting counts and percentages of subjects in corresponding categories. All possible categories defined in the CRF will be populated, even with zero counts. Percentages for missing values are omitted and do not account for the percent calculation of other categories. Percentages are based on the total category count, excluding the missing category if not otherwise mentioned. The total number of subjects is used as the denominator in certain tables (e.g., adverse events [AEs]). Footnotes will specify the percent basis in those cases.

Baseline summaries will be presented by treatment sequence and include a total summary column.

Individual subject data obtained from the eCRFs, external vendors, central clinical laboratory, central ECG laboratory, and any derived data will be presented by subject in data listings.

The version of the WHODrug and Medical Dictionary for Regulatory Activities (MedDRA) coding dictionaries used for coding of concomitant medications and medical histories, respectively, will be specified in the final Medical Coding Plan.

After all the data have been verified, coded if necessary, and entered into the database, a review will be performed.

The analyses described in this plan are considered a priori in that they have been defined before breaking the blind.

Any analyses performed after breaking the blind will be considered post hoc and exploratory. Post hoc analyses will be labeled as such on the output and identified in the CSR.

All analyses and tabulations will be performed using SAS® statistical software, version 9.4 or higher (SAS Institute Inc). Tables, listings, and figures will be presented in RTF format.

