#### 12.2.4 Patient Global Impression of Change (PGIC) Score and Clinical Global Impression of Change (CGIC) Score

The PGIC and CGIC will be completed on Day 14 of each treatment period.

The PGIC and CGIC are rating scales that assess the change in cough frequency since commencing study treatment.

[figure not shown]
Patient Global Impression of Change is a rating scale completed by subjects to assess change in cough frequency since commencing trial medication. It consists of a 7-point scale ranging from “very much improved” to “very much worse.” Clinician Global Impression of Change: A rating scale completed by Investigators to assess the subject's response to the trial treatment. It consists of a 7 point scale ranging from ‘very much improved’ to “very much worse.”

The PGIC and CGIC scores will be presented by frequency counts and percentages for each treatment group. The difference between treatment groups for PGIC and CGIC will be tested using the CMH row mean score difference test. The p-value for the difference will be presented.

The analysis will be repeated for the median, tercile and quartile group classifications based on the baseline awake cough frequency as described in the Key Secondary Efficacy Analyses section.

The PGIC and CGIC scores will also be remapped and given scores to create a continuous endpoint. A lower score will be considered a more positive outcome. The continuous endpoint will be summarized for each treatment group and appropriate hypothesis testing may be performed as a post-hoc analysis, if justified by the data.

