## **16. CHANGES TO PROTOCOL-SPECIFIED ANALYSES**

There are no changes to the planned analyses in the protocol.

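### For Global Rating of Change, PGIC and CGIC the SAP replaces the protocol's planned effect estimate and 95% CI with p-values only, and declares no change

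*SAP*

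**What the plan says.** Protocol section 4.2.3 lists "Global rating of change scores for cough severity and frequency" among the secondary endpoints, together with PGIC and CGIC. Section 10.6 names a method for awake and 24-hour cough frequency, the VAS and the CQLQ, and then covers the rest in one sentence: "Other efficacy endpoints will be summarized and analyzed to estimate the treatment effect and corresponding 95% confidence interval using a similar model" as for awake cough frequency. The synopsis repeats this. Section 10.2.1 adds that "all point estimates for the comparison between treatment groups will be accompanied by 2-sided 95% confidence intervals". Section 10.6 also says that the SAP governs statistical language.

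SAP section 12.2.3 treats the Global Rating of Change, for severity and for frequency, in three layers:

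- The three-category answer (*Worse*, *About the Same*, *Better*) gets a CMH row mean score test and a p-value.
- For the 14-level degree, "The degree of change will be summarized by frequency counts and percentages for each treatment group".
- A remapped numeric score is summarised by treatment, and "appropriate hypothesis testing may be performed as a post-hoc analysis, if justified by the data".

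SAP section 12.2.4 gives the 7-point PGIC and CGIC a pre-specified CMH row mean score test and a p-value. For their remapped version, "The continuous endpoint will be summarized for each treatment group and appropriate hypothesis testing may be performed as a post-hoc analysis", under the same condition on the data.

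SAP section 16 then states: "There are no changes to the planned analyses in the protocol".

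**The concern.** A p-value alone does not say how large a difference is or how precisely it was measured. In a Phase 2 crossover of about 50 subjects, the estimate and its interval are what a reader would carry forward from these ratings. The protocol promised both and the SAP plans neither.

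The finest-grained version of the Global Rating is also the one whose comparison is left open. SAP section 8 classes anything done after the blind is broken as post hoc and exploratory, and section 12.2.3 gives no criterion for when the data would justify a test. An estimate that the protocol planned could then be reported only as exploratory, if at all.

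Finally, a reader who relies on section 16 would believe that the protocol's analysis of these endpoints had been carried over intact.

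**Working it through.** The documents give no figure for this point to reproduce. The check is a comparison of text.

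**Step 1: which measures does the protocol's general sentence cover?** Section 4.2.3 lists 24-hour cough frequency, VAS, LCQ, CQLQ, Global Rating (severity and frequency), PGIC and CGIC. Section 10.6 gives its own method for 24-hour cough frequency, VAS and CQLQ. The remainder is LCQ, the two Global Rating items, PGIC and CGIC. No other protocol method exists for these five, so the sentence on other efficacy endpoints applies to them.

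**Step 2: what does the SAP plan for each?**

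| Measure | Pre-specified comparison in the SAP | Estimate and 95% CI |
|---|---|---|
| LCQ total score | Crossover mixed model | Yes (12.2.2) |
| Global Rating, 3 categories (severity; frequency) | CMH row mean score test | No |
| Global Rating, 14-level degree (severity; frequency) | None | No |
| Global Rating, remapped score | None; optional post hoc test | No |
| PGIC, 7-point | CMH row mean score test | No |
| CGIC, 7-point | CMH row mean score test | No |
| PGIC and CGIC, remapped scores | None; optional post hoc test | No |

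Of the five measures, LCQ keeps what the protocol planned. The other 5 − 1 = 4 do not.

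**Step 3: is the change declared?** Section 10 of the protocol allows the SAP to set out deviations. Section 16 of the SAP is where a reader would look for them, and it reports none. For these four measures that statement is inaccurate.

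**Step 4: is the numeric score defined?** SAP section 12.2.3 says that the Global Rating will be remapped to scores, with lower meaning better. The degree list has seven *better* levels (1 to 7) and seven *worse* levels (8 to 14), and no entry for *About the Same*. The readable text does not print the mapping, and the rating form is a figure that is not shown. The score for that answer is therefore unstated.

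**Step 5: can the protocol's model be applied?** The model in section 10.6 has sequence, period and treatment as fixed effects, subject within sequence as a random effect, and the period baseline as a covariate. These ratings are planned at the end of each treatment period (or at early withdrawal), so they have no baseline. Without that covariate, the rest of the model can be fitted to the scores that the SAP already creates.

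**The case against.** The strongest reply is that the SAP is entitled to do this. The protocol lets the SAP govern and lets it detail deviations. The cough-frequency model could not be copied literally, because these ratings have no baseline. A row mean score test is a recognised choice for ordered categories. The rule in protocol section 10.2.1 applies only where a point estimate exists. Counts, percentages and treatment-group summaries of the numeric score remain planned, any later test must be labelled exploratory, and the trial's primary endpoints concern safety.

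Most of that stands. It shows that a change of method is permitted and that its consequences are limited. It does not make section 16 accurate, because permission to detail a deviation is not met by stating that there is none. It also does not supply the estimate and interval that section 10.6 planned.

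Three stronger readings are tempting, and the documents do not support them:

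- *Every comparison of the graded scores is post hoc.* This is not so. PGIC and CGIC have a pre-specified test on their full 7-point scales, and the three-category Global Rating has one too. Only tests of the remapped scores are post hoc.
- *Subjects who answer About the Same have no score.* The SAP says that the scale will be remapped, and nothing rules out a middle value. Scoring an observed answer is not imputation, so SAP section 8.2 does not prevent it. The mapping is unstated, and no more than that can be said.
- *Testing three categories instead of the full degree scale loses a known share of information.* Any such figure needs a distribution of answers, and the documents give none. The argument would not reach PGIC and CGIC in any case, since they are tested on all seven levels.

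**Conclusion.** The point holds in this form. For four secondary measures (Global Rating for severity, Global Rating for frequency, PGIC and CGIC) the SAP puts CMH p-values in place of the protocol's model-based treatment effect and 95% CI. The 14-level degree of change has no planned comparison. Testing of the remapped scores waits on an undefined condition after unblinding, and the score for *About the Same* is not given in the readable text. Section 16 declares no change.

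The size is the count of four measures, and no distributional assumption is needed to reach it. It rests on two readings: that the protocol's sentence on other efficacy endpoints covers these measures, since no other method is named for them, and that no estimate or mapping sits in figures that are not shown. The primary safety endpoints and the key secondary cough-frequency analysis are unaffected. The SAP should be changed, but the trial's main conclusions do not depend on it.

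**What to change.** In SAP sections 12.2.3 and 12.2.4, replace the post hoc sentence with a pre-specified analysis:

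- State the score mapping. For the Global Rating, place *About the Same* between the better and worse levels: 7 + 1 + 7 = 15 levels, scored 1 to 15 with that answer at 8. Score PGIC and CGIC 1 to 7. Lower stays better throughout, as the SAP already intends.
- Fit the crossover mixed model to each score, with sequence, period and treatment as fixed effects, allowance for within-subject correlation, and no baseline covariate.
- Report the least-squares mean difference between ADX-629 and placebo with its 95% CI.
- Keep the CMH tests as supportive.

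Correct section 16 so that it declares any departure from protocol section 10.6 that remains. The amendment should be final before the blind is broken.

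The cost is SAP wording and four model fits on data already being collected. The downside is that ordered categories are treated as equally spaced scores. The SAP's own continuous endpoint already implies this, and the retained CMH results offer a supportive check.

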**Global Rating of Change Scores for Cough Severity and Frequency Scales:**

[figure not shown]

#### 12.2.4 Patient Global Impression of Change (PGIC) Score and Clinical Global Impression of Change (CGIC) Score

The PGIC and CGIC will be completed on Day 14 of each treatment period.

The PGIC and CGIC are rating scales that assess the change in cough frequency since commencing study treatment.

[figure not shown]
Patient Global Impression of Change is a rating scale completed by subjects to assess change in cough frequency since commencing trial medication. It consists of a 7-point scale ranging from “very much improved” to “very much worse.” Clinician Global Impression of Change: A rating scale completed by Investigators to assess the subject's response to the trial treatment. It consists of a 7 point scale ranging from ‘very much improved’ to “very much worse.”

The PGIC and CGIC scores will be presented by frequency counts and percentages for each treatment group. The difference between treatment groups for PGIC and CGIC will be tested using the CMH row mean score difference test. The p-value for the difference will be presented.

The analysis will be repeated for the median, tercile and quartile group classifications based on the baseline awake cough frequency as described in the Key Secondary Efficacy Analyses section.

The PGIC and CGIC scores will also be remapped and given scores to create a continuous endpoint. A lower score will be considered a more positive outcome. The continuous endpoint will be summarized for each treatment group and appropriate hypothesis testing may be performed as a post-hoc analysis, if justified by the data.

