Baseline for the above classifications will be the average of the pre-dose values in period 1 and period 2 for each subject.

The key secondary efficacy analysis of awake cough frequency will be repeated for the PP population.

Additionally, the number and percentage of subjects with  $\geq 30\%$ ,  $\geq 50\%$  and  $\geq 70\%$  reduction from baseline, at Day 14, will also be presented by treatment group.

Subjects will be classified as a responder/non-responder for each category ( $\geq 30\%$ ,  $\geq 50\%$  and  $\geq 70\%$  reduction) and treatment groups will be compared using a generalized estimating equation (GEE) for logistic regression with an exchangeable working correlation structure. The model will include fixed effects for treatment sequence [S1, S2], period [Period 1, Period 2] and treatment [ADX-629, placebo]. The period-specific baseline values will be included as a covariate. The odds ratio between ADX-629 and placebo, 95% confidence intervals for the odds ratio, and P-value for the covariate-adjusted treatment comparison will be presented.

Should the GEE model not converge, the model may be adjusted by removing factors or changing the correlation structure. If the GEE is found to be not appropriate for the data a Fisher's exact test will be used to calculate the odds ratio. The final model will be specified in the footnotes of the appropriate tables.

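### The CMH test for PGIC, CGIC and the 3-level Global Rating of Change items states no stratum, although each completer has a rating under both treatments; run as written, it ignores the pairing and can lose power

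*SAP*

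**What the plan says.** Each rating is collected once per treatment period. For the global impressions, "The PGIC and CGIC will be completed on Day 14 of each treatment period"; for the Global Rating of Change, "Subjects will complete the Global Rating of Change on Day 14 of each treatment period". A completer therefore has one rating under each treatment. CGIC is scored by the Investigator and the others by the subject, but all four are paired within subject.

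The comparison is the CMH row mean score test in both places: "The difference between treatment groups for PGIC and CGIC will be tested using the CMH row mean score difference test" in SAP 12.2.4, and for the 3-level items in 12.2.3 the CMH "row mean score difference test. The p-value for the difference will be presented". No stratum, subject term or period term is given there or in the general considerations of SAP section 8. In 12.2.4, "The analysis will be repeated for the median, tercile and quartile group classifications", and 12.2.3 has the same repeats. For the remapped scores, "appropriate hypothesis testing may be performed as a post-hoc analysis, if justified by the data".

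Protocol 10.6 planned something different: "Other efficacy endpoints will be summarized and analyzed to estimate the treatment effect and corresponding 95% confidence interval using a similar model" to that used for awake cough frequency. SAP section 16 declares no change from the protocol.

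**The concern.** A CMH test is defined by its strata. With subject as the stratum it is a valid matched test. With no stratum it compares two independent samples. The text allows either, so two programmers could follow it and report different p-values.

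Elsewhere the SAP writes the within-subject dependence out: correlated errors for cough frequency and an exchangeable GEE for responders (both 12.1.1). For these four tests it does not. At stake is the efficiency for which a crossover is chosen, and a p-value whose true error rate differs from the nominal 5%. The comparison also comes with no treatment difference and confidence interval, which the protocol had planned.

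**Working it through.** **The plan's own figure.** The only power statement (SAP section 5) is over 90% for improvements above 35%, for awake cough frequency. The readable text gives no SD, so it cannot be reproduced, and it does not bear on these ratings. No power is stated for PGIC, CGIC or Global Rating of Change.

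**Inputs from the documents.** About 50 randomized; two-sided 5% level; one rating per period; 7-point and 3-level scales; early-withdrawal ratings analyzed with Day 14 of the period concerned (SAP 8.3).

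**Assumptions.** The documents give no correlation, category proportions or effect size for these ratings. Assumed: 45 pairs plus 5 one-period subjects; latent bivariate normal ratings; placebo proportions 5/12/20/33/17/9/4% (7-point) and 30/50/20% (3-level); latent shift 0.4 SD; latent correlation 0 to 0.7.

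**Formulas.** With no stratum, CMH = (mean_A − mean_B)² / [s²(1/n_A + 1/n_B)], where s² is the variance of all ratings together. For n pairs with score correlation r, the true variance of the mean difference is 2σ²(1 − r)/n, but the test uses about 2σ²/n. Its true size is therefore about 2[1 − Φ(1.96/√(1 − r))].

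With subject as stratum, a pair with difference d contributes d/2 to the numerator sum and d²/4 to the variance, so CMH = (Σd)² / Σd². A subject with one rating contributes nothing.

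**Analytic check.** On a 7-point scale with proportions 5/10/20/35/15/10/5% and 50 pairs, latent correlations of 0.3 and 0.5 give score correlations of 0.28 and 0.47. Then 1.96/√0.72 = 2.31, giving 2.1%, and 1.96/√0.53 = 2.69, giving 0.7%. Simulation gives 2.1% and 0.8%.

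**Simulation, 45 pairs plus 5 one-period subjects** (about ±1 point for power):

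| Latent correlation | 7-point power, no stratum | 7-point power, by subject | 7-point size, no stratum | 3-level power, no stratum | 3-level power, by subject |
|---|---|---|---|---|---|
| 0 | 47% | 44% | 5% | 41% | 38% |
| 0.1 | 46% | 47% | 4% | 40% | 40% |
| 0.3 | 46% | 56% | 2% | 39% | 48% |
| 0.5 | 45% | 70% | 1% | 38% | 58% |
| 0.7 | 45% | 88% | 0.1% | 36% | 72% |

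On the 7-point scale the gain from stratifying is 47 − 46 = 1 point at 0.1, 56 − 46 = 10 at 0.3 and 70 − 45 = 25 at 0.5. At zero correlation stratifying costs 47 − 44 = 3 points. At a correlation of −0.2 the unstratified size rises to about 7%.

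**Other inputs.** With 50 pairs, a 0.5 SD shift and the proportions of the analytic check, the 7-point powers at correlation 0.5 are 73% and 90%. With 38 pairs plus 12 one-period subjects (0.4 SD, correlation 0/0.1/0.3/0.5), they are 44/43/43/42% against 37/41/49/62%, so the break-even moves above 0.1.

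**Crossover model on the scores** (REML, sequence, period, treatment, within-subject correlation; 45 + 5 subjects; correlation 0/0.1/0.3/0.5/0.7): power 46/49/58/71/88% (7-point) and 41/42/49/58/72% (3-level), size 4.7–5.3%, 95% CI coverage 94.4–95.5%.

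**Period effect of 0.4 SD, correlation 0.3–0.5.** Size of the subject-stratified CMH is 3.6–4.2% with sequences of 23/22 and 5.5–6.1% with 27/18. The model stays at 4.8–5.2% in both.

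**The case against.** The SAP never says that the test is unstratified. A reader might infer that it prescribes an independent-samples analysis, but the text does not support that. Since the SAP models dependence elsewhere, stratification by subject may be what was meant. The table index in Appendix C and some figures are not readable here, so a stratum stated there cannot be excluded. This stands: the defect is an omission, and the power loss follows only if the test is run without a stratum.

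A reader might also infer a risk of false claims of benefit. Under positive correlation the unstratified test is conservative, so that reading fails; only negative correlation would inflate the error rate.

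The size of the loss rests on an undocumented correlation, is negligible near 0.1, and touches only secondary endpoints in a trial whose primary endpoints are safety. All of that stands.

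Nor is subject stratification free of cost. It gives no weight to one-period ratings, which SAP 8.3 keeps and which belong to the ITT population, and it does not adjust for period. That is why the crossover model is the better first choice.

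Finally, the protocol lets the SAP govern statistical wording, so departing from protocol 10.6 is permitted. What remains is that section 16 does not declare it. It would also be too strong to say that no measure of size is planned: percentages by treatment and summaries of remapped scores are. What is missing is a between-treatment estimate with its interval.

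**Conclusion.** The point holds as a gap in specification with a real but bounded consequence. For four secondary comparisons the SAP names a test without the element that decides whether the pairing is used. Run with no stratum, the test is valid but conservative under positive within-subject correlation. Under the stated assumptions it gives up about 10 points of power at a latent correlation of 0.3 and 25 at 0.5 on the 7-point scale, and nothing at or below about 0.1. More one-period subjects raise that break-even. The direction follows from the variance formula; the amounts depend on assumed correlation, proportions, shift and dropout. The primary safety analyses, the key secondary mixed model and the responder GEE are unaffected.

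**What to change.** In SAP 12.2.3 and 12.2.4, replace the CMH test with, or make primary, a linear crossover model on the scored rating: fixed effects for sequence, period and treatment, with within-subject correlation, reporting the treatment difference and 95% CI. No baseline covariate is needed, because these ratings have no baseline. This is in line with protocol 10.6, keeps one-period and early-withdrawal ratings, and adjusts for period. For the 3-level items, state the integer scores, because 12.2.3 does not clearly say that they, rather than only the 14-level degree scale, are remapped.

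If CMH is kept, state that it is stratified by subject, including in the median, tercile and quartile repeats. Pairs stay intact there, because "Baseline for the above classifications will be the average of the pre-dose values in period 1 and period 2 for each subject". Say openly that one-period subjects then drop out of the test and that period is not adjusted for. If only a p-value is to be reported, list that change in SAP section 16.

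The cost is a few sentences in two SAP sections and a short model program, or one strata term if CMH is kept. No new data are needed. SAP section 8 labels analyses performed after the blind is broken as post hoc, so the edit should precede unblinding.
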